9.3. Serious Adverse Advents (SAE)

All events which meet the definition of serious will be collected and recorded in the participant notes and the Case Report Form (CRF). SAEs will in addition be reported to the trials office immediately and within 24 hours of being made aware of the event.

An SAE is an untoward event which:

- Results in death.
- Immediately threatens the life of the participant*.
- Results in hospitalisation or a longer than anticipated stay in hospital.
- Results in a persistent or significant disability.

*Life-threatening in the definition of a Serious Adverse Event or Serious Adverse Reaction refers to an event in which the participant was at risk of death at the time of the event. It does not refer to an event which hypothetically might have caused death if it were more severe. Important adverse events/reactions that are not immediately life-threatening or do not result in death or hospitalisation, but may jeopardise the participant or may require intervention to prevent one of the other outcomes listed in the definition above, should also be considered serious.

9.4. Reporting period

The reporting period for AEs is up to 6 weeks post-surgery.

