3.4. Assessment of Risk

The safety of the ultrasound is well established. The current consensus is there are no negative side effects to the patient if performing diagnostic ultrasound according to current regulatory guidelines (15).

The risks of the surgical management of miscarriage are outlined within the Royal College of Obstetrics and Gynaecology consent for surgical evacuation of the uterus for early pregnancy loss (16). The serious risks include: uterine perforation (5 in 1000 women) which may require laparoscopy or laparotomy to diagnose or treat organ injury; significant trauma to the cervix (1 in 1,000 to 10,000). Frequent risks include: bleeding that lasts for up to two

weeks is very common but bleeding leading to blood transfusion is uncommon (1-2 in 1,000 women); pelvic infection (3 in 100 women); repeat surgical management (5 in 100 women).

The alternatives include medical management with mifepristone and prostaglandins or expectant management, particularly without an intact gestational sac. These alternatives are associated with heavier and longer bleeding and a 15-50% chance of requiring surgical treatment either as an emergency or the woman's preference.

This trial is categorised as:

Type A: No higher than the risk of standard medical care

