4. ELIGIBILITY

4.1. Inclusion Criteria

- Aged 16 years or over.
- Referred for surgical evacuation of products of conception.
- Willingness to be randomised between treatment modalities.
- Willingness to undergo office hysteroscopy 4-8 weeks following surgical management of miscarriage.
- Written informed consent obtained prior to surgical evacuation.

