8. OUTCOME MEASURES AND STUDY PROCEDURES

8.1. Clinical assessments and procedures

Procedural and baseline information will be collected prospectively during the intervention. Researchers will input the data directly onto a specifically created case report form. Baseline demographic information will include the patient's age, BMI, gestation, parity, if general anaesthesia is to be used, and type of miscarriage. The type of miscarriage included in this trial will be those diagnosed with early embryonic demise which is a delayed or missed miscarriage: The NICE guidance will be followed for the diagnosis of miscarriage (See box 1).

Following randomisation, the surgical procedure for the management of miscarriage will be conducted with or without intraoperative ultrasonography

Two to four weeks later, patients will be contacted to assess whether they have developed an infection after the procedure.

Four to eight weeks after the procedure, patients will undergo a follow-up hysteroscopy in the office setting without general anaesthesia. This is solely to identify if any intrauterine adhesions have formed following the surgical management of miscarriage. This is an important outcome because the prevalence of intrauterine adhesions is underestimated by clinicians and is thought to be related to the number of curette insertions and how vigorously the curettage in performed [18,19]. Two cohort studies reported 8-19% of women had intrauterine adhesions after surgical management of miscarriage [18,19]. Moreover, intrauterine adhesions can lead to menstrual disorders, infertility, pelvic pain and endometriosis.

Box 1. NICE guidance for diagnosis of non-viable intrauterine pregnancy

1.4.5

When performing an ultrasound scan to determine the viability of an intrauterine pregnancy, first look to identify a fetal heartbeat. If there is no visible heartbeat but there is a visible fetal pole, measure the crown–rump length. Only measure the mean gestational sac diameter if the fetal pole is not visible. 1.4.6

If the crown-rump length is less than 7.0 mm with a transvaginal ultrasound scan and there is no visible heartbeat, perform a second scan a minimum of 7 days after the first before making a diagnosis. Further scans may be needed before a diagnosis can be made.

1.4.7

If the crown-rump length is 7.0 mm or more with a transvaginal ultrasound scan and there is no visible heartbeat:

- seek a second opinion on the viability of the pregnancy and/or

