8.4.5. Post-operative complications

With the exception of intrauterine adhesions, these will need to have occurred within two weeks of treatment and are assessed 2-4 weeks following the procedure. Post-operative complications are defined as any of the following:

- Infection, with a definition based on CDC criteria and other studies as **two** or more of the following (without any **other** obvious cause of infection on history and examination): (1) uterine tenderness, (2) offensive vaginal discharge, (3) high temperature (4) white blood cell count > 12×10^9 /L. To assess this, the patient will be contacted and asked whether they have suffered from: (1) pelvic pain beyond two days of the surgery, (2) offensive vaginal discharge, (3) fever or chills. If they report two or more of these patient-related symptoms then they will be invited in for clinical assessment in line with good clinical practice
- Haemorrhage requiring blood transfusion
- Disseminated intravascular coagulation
- Unplanned hospital admission due to a post-operative complication
- Intrauterine adhesions (defined as the formation of any filmy adhesions) identified at 4-8 weeks following the procedure with hysteroscopy. Pictures of the uterine cavity will be taken and passed on to hysteroscopists blinded to the randomisation. There will be up to five hysteroscopists who will make a majority decision on the presence of the intrauterine adhesions.
- Death

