8.5. Schedule of Assessments

Visit	Screening (Randomisation, surgery treatment forms)	Visit for surgery (Two week follow-up form)	2-4 weeks post- operative	4-8 weeks post- operative (Hysteroscopy treatment form)
Eligibility check	X			
Relevant medical history taken	x			
Concomitant medication	x	x	x	x
Valid informed consent		x		
Randomisation		X		
Surgical management of miscarriage		x		
Adverse events	x	x	x	x
Collection of outcome data		x		x
Telephone/ In person follow-up			x	
Follow-up office hysteroscopy				x
Site staff interview				x

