9.2. Adverse Events (AE)

There are certain AEs which are commonly expected in participants undergoing surgical management of miscarriage. As these events are well characterised, it is highly unlikely that this trial will reveal any new safety information relating to this intervention. The recording of selected AEs will therefore not affect the safety of participants or the aims of the trial.

AE that will be recorded in the Case Report Form (CRF) will include: uterine perforation, cervical trauma, bladder injury, complications of anaesthesia, anaphylaxis, disseminated intravascular coagulation, bleeding (as estimated blood loss in ml and those women requiring blood transfusion), repeat surgical evacuation, pelvic infection, repeat evacuation needed, unplanned hospital admission and intrauterine adhesions (Asherman's syndrome).

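### The 6-week end of adverse event reporting conflicts with the trial-only hysteroscopy at 4-8 weeks and with the adverse event row at that visit

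*Protocol*

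**What the plan says.** Section 9.4 is the only place where the protocol gives an adverse event reporting period: "The reporting period for AEs is up to 6 weeks post-surgery".

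Section 8.1 sets the last study visit: "Four to eight weeks after the procedure, patients will undergo a follow-up hysteroscopy in the office setting without general anaesthesia". It gives the purpose as research only: "This is solely to identify if any intrauterine adhesions have formed following the surgical management of miscarriage". Section 4.1 makes it an entry condition: "Willingness to undergo office hysteroscopy 4-8 weeks following surgical management of miscarriage".

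The Schedule of Assessments in 8.5 has the row "Adverse events x x x x". The fourth mark falls in the 4-8 week column, the hysteroscopy visit. No contact is scheduled after that visit.

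Section 9.2 lists the adverse events to be recorded. The list includes uterine perforation, cervical trauma and pelvic infection, and ends with "unplanned hospital admission and intrauterine adhesions (Asherman's syndrome"). Section 8.4.5 defines adhesions as an outcome "identified at 4-8 weeks following the procedure with hysteroscopy", and requires the other post-operative complications to have occurred within two weeks of treatment.

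Section 9.3 collects all serious events and gives no end date. Section 9.5.2 describes SAEs as a subset of adverse events. The definitions table treats an event as related if any research procedure caused it.

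**The concern.** The hysteroscopy is an invasive procedure that participants undergo because they are in the trial. Its complications therefore belong in the trial's safety reporting. A reporting period that closes before the visit window closes puts part of that reporting in doubt.

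Two things are at stake. First, sites may act differently: one following 9.4 would stop at week 6, while one following 8.5 would record events at a week-7 visit. The SAE rate is a secondary outcome (8.4.2), so it could be counted over different periods at different sites. Second, section 2.1 requires the pilot to judge whether its protocol, hysteroscopy included, can be carried into a substantive trial. That judgement needs a clear record of what the hysteroscopy itself causes.

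**Working it through.** The protocol gives no figure to reproduce, so the check compares time windows and then reads the sections side by side.

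**Inputs**
- End of adverse event reporting: week 6 (9.4).
- Hysteroscopy window: weeks 4 to 8 (4.1, 8.1, 8.4.5).
- Planned enrolment: 90 (13.1).
- Expected follow-up: at least 80% (8.2).
- Adhesion prevalence cited by the protocol: 8-19% (8.1).
- Timing of visits within the window: not given. An even spread is assumed, with a range of 25% to 75% of visits after week 6.

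**Share of the window after the cut-off**

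(8 − 6) / (8 − 4) = 2/4 = 50%.

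**Number of hysteroscopies after the cut-off**

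Women followed up at 80%: 0.80 × 90 = 72.

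| Share of visits after week 6 | Of 72 (80% follow-up) | Of 90 (full follow-up) |
|---|---|---|
| 25% | 18 | 22.5 |
| 50% (even spread) | 36 | 45 |
| 75% | 54 | 67.5 |

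**Reporting time left after a hysteroscopy at week t**

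This is 6 − t weeks for t up to 6, and zero after that: 2 weeks for a visit at week 4, 1 week at week 5, and none from week 6 on. Earlier visits are therefore covered only in part.

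**Would another route capture these events?**
- Post-operative outcome list (8.4.5): no. Apart from adhesions, events count only within two weeks of treatment, and the hysteroscopy is at week 4 at the earliest. An infection or an unplanned admission after hysteroscopy is not picked up there.
- Intraoperative list (8.4.4): this covers perforation and cervical damage, but reads as the list for the evacuation.
- Schedule (8.5): the mark at the visit can catch events up to and during it. With no later contact, it gives no scheduled route for delayed ones.
- SAE reporting (9.3, 9.5.2): possibly. Section 9.3 has no end date and 9.5.2 starts the reporting clock when the site becomes aware. But since 9.5.2 treats SAEs as a kind of adverse event, a site could reasonably apply the 9.4 limit to them.

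**Adhesions**

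With an even spread and 72 visits, 36 × 0.08 = 2.9 to 36 × 0.19 = 6.8, so about 3 to 7 women would have adhesions found after week 6. They are outcome events by definition (8.4.1, 8.4.5), and 8.5 marks collection of outcome data at that visit. Only their second listing as an adverse event under 9.2 is in doubt.

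**The case against.** The strongest reply is that 8.5 marks adverse events at the hysteroscopy visit, so the protocol intends to collect them and 9.4 is a one-line mismatch. The pilot is small and descriptive, and both arms have the same hysteroscopy and the same cut-off, so the comparison between arms is not obviously distorted. Much of this stands: the protocol contradicts itself and does not settle on exclusion. It does not remove the point, because 9.4 is the section that sets the period, and 8.5 schedules no contact after the visit.

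A reader might infer more than the protocol supports:
- *Harms of hysteroscopy go systematically unreported.* Not shown. Events up to week 6 are reportable on any reading, and 8.5 points to collection at later visits.
- *Adhesions found in weeks 6-8 are lost.* They are not. They count in the primary composite.
- *The SAE rate is truncated.* This is possible but not stated, since 9.4 speaks of adverse events and 9.3 sets no end.
- *Perforation at hysteroscopy contaminates the composite.* Section 8.4.1 gives no time or procedure limit for genital tract damage, but 8.4.4 lists perforation and cervical damage as intraoperative, which largely answers this.
- *The risk category in 3.4 is wrong.* Section 3.4 concludes "Type A: No higher than the risk of standard medical care" without mentioning the hysteroscopy. That is an omission. The protocol gives no hysteroscopy risk figure, so nothing in it shows the category to be mistaken.

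**Conclusion.** The point holds as a contradiction that should be corrected. Section 9.4 is incompatible with the 4-8 week hysteroscopy window and with the adverse event row in 8.5. Followed literally, it drops complications of a research procedure in half of its permitted window, and cuts short observation after the earlier ones. Whether SAEs are also limited is unclear.

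The figure of about 36 of 72 hysteroscopies after the cut-off rests on 80% follow-up and an even spread of visits. The range is 18 to 54 of 72. Section 2.1 refers to adhesions at 6 weeks, so visits may cluster near the cut-off, where little or no reporting time remains afterwards. The protocol gives no complication rate for office hysteroscopy, so the number of events at risk of being missed cannot be stated.

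**What to change.** 1. Reconcile 9.4 with 8.1 and 8.5. State that adverse event and SAE reporting runs through the hysteroscopy visit and a post-procedure interval set by the sponsor, and state when it ends for women who do not attend.
2. Apply the same period to the SAE-rate outcome in 8.4.2, so that all sites count over the same time.
3. Record whether each event is attributed to the evacuation or to the hysteroscopy. The definitions table covers any research procedure, whereas 9.6 ties relatedness to the intervention, so attribution should not be left to inference.
4. Minor clarifications: cross-refer the genital tract damage component in 8.4.1 to the intraoperative list in 8.4.4, and mention the hysteroscopy in 3.4.

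The cost is amendment wording, possibly one case report form field (the form is not shown, so it may already exist), and a few more events to process. Sample size and analysis are unaffected.

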9.5. Reporting period – At Site

9.5.1. Adverse Events

Selected AEs should be recorded in accordance with the AE CRF. Records of AEs should be submitted via the trial electronic Remote Data Capture system (eRDC) as soon as possible.

9.5.2. Serious Adverse Events

AEs defined as serious and which require reporting as an SAE should be reported on an SAE Form. When completing the form, the PI will be asked to define the causality and the severity of the AE.

Category	Definition	Causality	
Definitely	There is clear evidence to suggest a causal relationship, and other possible contributing factors can be ruled out		
Probably	There is evidence to suggest a causal relationship, and the influence of other factors is unlikely		
Possibly	There is some evidence to suggest a causal relationship, however, the influence of other factors may have contributed to the event (e.g. the patient's clinical condition, other concomitant events or medication)		
Unlikely	There is little evidence to suggest there is a causal relationship; there is another reasonable explanation for the event (e.g. the patient's clinical condition, other concomitant events or medication)	Unrelated	
Not related	There is no evidence of any causal relationship		

On becoming aware that a participant has experienced an SAE, the Investigator or delegates(s) should report SAE to their own Trust in accordance with local practice and to the BCTU trials office.

To report an SAE to the BCTU trials office, the Investigator or delegates(s) must complete, date and sign the trial specific BCTU SAE form. The completed form should be faxed or emailed to the BCTU trials team using one of the numbers listed below as soon as possible and no later than 24 hours after first becoming aware of the event:

To report an SAE, fax or email the SAE Form to:

[name]

[contact]

On receipt of an SAE form, the BCTU trials team will allocate each SAE a unique reference number and return this via fax or email to the site as proof of receipt. If the site has not received confirmation of receipt of the SAE from the BCTU or if the SAE has not been assigned a unique SAE identification number, the site should contact the BCTU trials team within 1 working day. The site and the BCTU trials team should ensure that the SAE reference number is quoted on all correspondence and follow-up reports regarding the SAE and filed with the SAE in the Site File.

Where an SAE Form has been completed by someone other than the Investigator, the original SAE form will be required to be countersigned by the Investigator to confirm agreement with the causality and severity assessments.

9.5.3. Provision of follow-up information

Following reporting of an SAE for a participant, the participants should be followed up until resolution or stabilisation of the event. Follow-up information should ideally be provided on a DCF, using the SAE reference number provided by the BCTU trials team. Once the SAE has been resolved, all follow-up information has been received and the paperwork is complete, the original SAE form that was completed at site must be returned to the BCTU trials office and a copy kept in the Site File.

9.6. Reporting Procedure – BCTU Trials Team

On receipt of a faxed SAE form from the site, the BCTU trials team will allocate each SAE form with a unique reference number and enter this onto the SAE form in the section for office use only. The SAE form (containing the unique reference number completed) will be forwarded to the site as proof of receipt within 1 working day. The SAE reference number will be quoted on all correspondence and follow-up reports regarding the SAE and filed with the SAE in the TMF.

On receipt of an SAE Form, the Chief Investigator (CI) or delegate(s) will independently determine the seriousness and causality of the SAE. An SAE judged by the PI or CI or delegate(s) to have a reasonable causal relationship with the intervention will be regarded as a related SAE. The causality assessment given by the PI will not be downgraded by the CI or delegate(s) If the CI or delegate(s) disagrees with the PI's causality assessment, the opinion of both parties will be documented, and where the event requires further reporting, the opinion will be provided with the report.

The CI or delegate(s) will also assess all related SAEs for expectedness. If the event is unexpected (i.e. is not defined in the protocol as an expected event) it will be classified as an unexpected and related SAE.

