Policies	POL	Policies are developed to describe the approach of the University of Birmingham UoB on areas that heavily regulated. Policies may also be developed when there is ambiguity in how regulatory requirements should be implemented in the QMS or when procedures to be captured in the QMS address areas controversial within the UoB at the time of implementation. Policies explain why the UoB has its procedures, especially when they seem to deviate from the regulatory requirements. Policies should be read in conjunction with the relevant SOP. Policies that are not part of a Quality Manual are coded up as 'POL'.
Quality Control Documents	QCD	Quality Control Documents can be instructions, forms, templates or checklists. They are developed to share best practices, promote standardisation to guarantee quality standards are maintained and reduce resources otherwise needed to develop similar documents. Unless indicated otherwise in the relevant SOP, QCDs are not mandatory and are designed to be an optional aid to UoB staff.
Quality Management System	QMS	A Quality Management System (QMS) is a system that includes procedures

IRAS ID: 253447

		and policies to describe how certain tasks should be performed and that encapsulate any standards and/or regulatory requirements that may apply to those tasks. By adhering to the Quality Management System, the user and the UoB will be assured that applicable regulations are adhered to.	
Standard Operating Procedures	SOP	Standard Operating Procedures are detailed written instructions to achieve uniformity in the performance of a specific function. They define tasks, allocate responsibilities, detail processes, indicate documents and templates to be used and cross- reference to other work instructions and guidance or policy documents. They are standards to which the UoB may be audited or inspected.	
Adverse Event	AE	Any untoward medical occurrence in a participant or clinical trial subject participating in the trial which does not necessarily have a causal relationship with the intervention received.	
Related Event		An event which resulted from the administration of any of the research procedures.	

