Serious Adverse Event	SAE	 An untoward occurrence that: Results in death Is life-threatening* Requires hospitalisation or prolongation of existing hospitalisation Results in persistent or significant disability or incapacity Consists of a congenital anomaly/ birth defect Or is otherwise considered medically significant by the Investigator** 	
Unexpected and Related		An event which meets the definition	

Event		of both an Unexpected Event and a Related Event.
Unexpected Event		The type of event that is not listed in the protocol as an expected occurrence.
Source data		All information in original records and certified copies of original records of clinical findings, observations, or other activities in a clinical trial necessary for the reconstruction and evaluation of the trial.
Birmingham Clinical Trials Unit	BCTU	The co-ordinating centre for the trial.

TRIAL SUMMARY

Title: SEE U: Surgical Evacuation with intraopErative Ultrasound

Objectives: To test the premise that intraoperative ultrasound can reduce the incidence of early and late complications following surgical removal of products of conception.

Trial Design: Prospective, pilot, 2 arm, multicentre, randomised, open clinical trial to assess feasibility.

Participant Population and Sample Size: Women aged 16 years or over that are referred for surgical management of miscarriage. The required sample size is 90 patients.

Eligibility Criteria

Inclusion criteria:

- Aged 16 years or over.
- Referred for surgical evacuation of products of conception.
- Willingness to be randomised between treatment modalities.
- Willingness to undergo office hysteroscopy 4-8 weeks after surgical management of miscarriage.
- Written informed consent obtained prior to surgical evacuation.

Exclusion criteria:

- Incomplete or retained products of conception will be excluded from the trial as there are no widely used criteria for deciding which women should have surgical evacuation
- Suspicion of malignant gestational disease.

Intervention: Surgical evacuation of products of conception with intraoperative ultrasonography.

Comparator: Surgical evacuation of products of conception without intraoperative ultrasonography.

Outcome Measures:

Process outcomes

To obtain estimates for important aspects of the protocol to allow development of a substantive trial, specifically:

- 1. To derive real-time data on the design aspects of the study:
 - I. Proportion of eligible women of those screened.

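### Section 9.6 ties a related SAE to the intervention while the definitions table covers any research procedure, so a serious injury from the trial-only hysteroscopy can miss the 15-day REC report

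*Protocol*

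**What the plan says.** The protocol words relatedness in two ways.

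- The definitions table describes a Related Event as "An event which resulted from the administration of any of the research procedures". An Unexpected and Related Event must meet the definition "of both an Unexpected Event and a Related Event", so it takes over the wider wording. Section 9.1 refers readers to this table for the types of adverse event.
- Section 9.6 sets out what happens when an SAE form arrives. An SAE that the PI, the Chief Investigator or a delegate judges to "have a reasonable causal relationship with the intervention will be regarded as a related SAE". Expectedness is then assessed for related SAEs.

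Section 9.7.1 sends SAEs that are both unexpected and related to the REC within 15 days.

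On the hysteroscopy, section 8.1 says: "Four to eight weeks after the procedure, patients will undergo a follow-up hysteroscopy in the office setting without general anaesthesia". Of its purpose it says: "This is solely to identify if any intrauterine adhesions have formed following the surgical management of miscarriage". Willingness to have it is an inclusion criterion in section 4.1.

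Section 9.2 introduces the adverse events to be recorded with "There are certain AEs which are commonly expected in participants undergoing surgical management of miscarriage". Its list includes uterine perforation and pelvic infection. Section 3.4 discusses the risks of ultrasound and of surgical evacuation, does not mention the hysteroscopy, and assigns "Type A: No higher than the risk of standard medical care".

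**The concern.** The hysteroscopy is an invasive procedure that participants in both arms undergo because they are in the trial. An ethics committee has a direct interest in serious harm from a procedure of that kind. If the working rule in section 9.6 asks only about the intervention, and the hysteroscopy is not part of it, such harm can be filed as unrelated at the first step and go no further. What is at stake is expedited safety reporting and the REC's view of the added research burden. No estimate of treatment effect or of feasibility is affected.

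**Working it through.** No figure in the protocol needs reproducing. The check sets the passages side by side and follows one event through them.

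**1. What the word intervention covers.**
- Trial Summary: "Intervention: Surgical evacuation of products of conception with intraoperative ultrasonography". The hysteroscopy is not included.
- Section 7, whose title pairs trial treatment with intervention, covers the surgical procedure (7.1) and the ultrasound (7.2). It does not describe the hysteroscopy.
- Section 8.1 has procedural data collected during the intervention. That means the surgery, in either arm. The hysteroscopy comes later in the same section, as follow-up.
- Section 9.2 moves from surgical management of miscarriage to safety information on this intervention. Again that means the surgery.

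The scope varies between surgery with ultrasound and surgery in either arm. None of the four includes the hysteroscopy.

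**2. One event under both rules.** Suppose a woman is admitted to hospital in week 5 because of a uterine perforation caused by the hysteroscopy. Admission makes it serious under section 9.3.
- Definitions table: it resulted from a research procedure, so it is related.
- Section 9.6 read literally: the cause was not the intervention, so the stated test is not met.
- Next step in section 9.6: expectedness is assessed for related SAEs, so this one is not assessed.
- Section 9.7.1: the event is not categorised as unexpected and related, so no 15-day report follows.

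**3. Whether the causality form settles it.** The category table in section 9.5.2 grades the strength of a causal relationship but does not say with what. It leaves the conflict open.

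**4. The same event if it is accepted as related.** Section 9.6 asks whether the protocol defines the event as expected, and the definitions table frames expectedness by type of event, not by cause. The section 9.2 list names uterine perforation and pelvic infection without tying either to a procedure. An assessor could therefore class a hysteroscopic perforation as expected, and the 15-day report would again not be made. Correcting the relatedness wording alone does not close the gap.

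**5. Exposure.** The target is 90 women (section 13.1), all of whom must be willing to have the hysteroscopy (section 4.1). Section 8.2 expects follow-up of at least 80%: 90 × 0.80 = 72. So between 72 and 90 women would have the procedure if that expectation is met. The protocol gives no hysteroscopy complication rate, so this is a count of women exposed and not of events.

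**The case against.** The best defence is that section 9.6 states a sufficient condition. It says which SAEs will be regarded as related, not that all others are unrelated. Section 9.1 points to the definitions table, and the term that triggers the REC report is defined there in the wider sense. A PI who applies the table would call the injury related, and section 9.6 bars the Chief Investigator from downgrading that judgement. Beyond this, every SAE goes to the trials office within 24 hours (9.3, 9.5.2), the independent oversight committee reviews every SAE (9.9), and a significant safety issue goes to the REC immediately (9.7.2).

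Much of this stands, and it is why the event *can* miss the report; it does not follow that it *will*. But section 9.6 offers no other route to related, and its sentence frames the PI's own judgement in terms of the intervention. The no-downgrade rule helps only if the PI has already used the wider test. Committee review is not a REC report, and section 9.7.2 depends on someone judging the matter significant. None of these guarantees a report of the individual event.

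On expectedness, the opening sentence of section 9.2 refers to surgical management of miscarriage, so a careful assessor may confine the list to the evacuation. That is a fair reading, but the text does not require it.

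A reader might infer more than the text supports:
- *That control women can never have a related SAE.* This rests on the Trial Summary label alone. Sections 7, 8.1 and 9.2 use the word for the surgery given in both arms.
- *That PIs would not hear of such an event.* Section 9.8 also covers any other safety issue arising in the trial.
- *That the omission in section 3.4 carries through to monitoring.* Sections 11.2 and 11.3 rest on a risk assessment and a monitoring plan that are not shown, and nothing identifies section 3.4 as that assessment.
- *That the pilot sets out to show the hysteroscopy is safe enough for a larger trial.* Section 2.1 asks whether outcome tools and processes are acceptable and adequate.

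**Conclusion.** The conflict is in the text and should be corrected. Section 9.6 and the definitions table give different answers for the same serious hysteroscopy injury, and under section 9.6 the event can miss both the expectedness assessment and the 15-day REC report. The section 9.2 list adds a second way to miss it, because the injury could be classed as expected. Section 3.4 assigns its risk category without mentioning the procedure. That is an omission to repair; it does not show that Type A is wrong.

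The conclusion assumes that section 9.6 is applied as worded and that intervention has one of the meanings the protocol gives it. The size is bounded by exposure: 90 women asked, and at least 72 examined if the follow-up expectation is met. How many serious events would be affected cannot be estimated from the protocol, and the number may be zero.

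The point concerns classification. Whether the six-week reporting period in section 9.4 fits a hysteroscopy done as late as eight weeks is a separate matter.

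**What to change.** 1. In section 9.6, replace the reference to the intervention with: *with any of the research procedures (including the surgical evacuation, intraoperative ultrasound and follow-up hysteroscopy)*. This matches the definitions table and names the procedures, so that their status is not in doubt.
2. Add a field to the SAE form recording which procedure the causality assessment refers to.
3. State that the section 9.2 list defines expectedness for the evacuation only, so that an event caused by the hysteroscopy is not expected merely because its type appears there.
4. Have section 3.4 consider the hysteroscopy and then confirm or revise Type A.

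The cost is a protocol amendment of a few lines and one form field. There may be some additional expedited reports. The trial's design, sample size and analysis do not change.
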